## 9.5 DOSE PROPORTIONALITY FOR MARZAA

Analysis of dose proportionality in Part 2 will be performed by a repeated measures ANOVA model using the SAS Proc Mixed procedure if sufficient number of data points for different dose levels for SC injection route only are available. The analysis will be performed using the loge-transformed, dose-normalized, Cmax/D and Cmin/D as dependent variable, visit (Days 7, 14, 21, 28, and 50 relative to start of dosing for dose level 1 or day of dose escalation) and treatment as fixed effect. VisitVisit will be specified as repeated measurement. Subject as random effect.

The comparison will be performed for at least 2 dose levels with at least 6 subjects of PK data available (Cmin or Cmax values for each time point). Pair-wise comparisons will be made between test dose levels of 60, 90 and 120 µg/kg and the reference dose group of 30 µg/kg.

95% CIs for the geometric mean ratios (GMRs) will be obtained from the mixed-effects model. The formula for the calculation of the estimated ratio between the test and reference and the (1-2\*α)\*100 % CI of the ratio is given below.

- Difference = Estimate of difference between test and reference LSMs

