Dose interruption and surgery: Daily SC study injections will be interrupted, as needed, if there is a need for a surgical procedure; an event requiring extended (>48 hours) hospitalization; a thrombotic event; clinical evidence of inhibitor formation; or laboratory results suggesting an antibody may be developing.

Measurements:

MarZAA antigen and activity levels, as well as coagulation parameters, will be measured during Part 2 of the study at Day 1 (At pre-dose and Hour 7 post-dose, Day 3 (Pre-dose), Day 5 (Pre-dose), Day 7 (Pre-dose and Post-dose Hour 7).

MAA-201 VERSION 2.0

If no spontaneous bleeding occurs at the first dose level in part 2 of the study, trough antigen and activity, as well as coagulation parameters, will be measured on days 14, 21, 28, and 50 after starting their dosing regimen.

If spontaneous bleeding occurs after the fifth daily dose at any dose level, MarzAA antigen and activity levels will be measured within 6 hours of the spontaneous bleed (if feasible). Specimens for coagulation and immunogenicity testing will also be drawn.

Once it is determined to escalate to the next dose level, a pre-dose and Hour 7 post-dose specimen, will be drawn for PK, coagulation, and thrombogenicity markers on Day 7 *after* the dose has been escalated to estimate the *new* trough and peak concentrations (PCs) and PD. MarzAA antigen and activity levels, as well as coagulation parameters, will then be measured (pre-dose) at Day 14, 21, 28, and 50 after dose escalation.

Immunogenicity assays: Specimens for immunogenicity testing (antibody to MarzAA, neutralizing activity, cross reactivity) will be drawn at screening, Part 1a pre-dose, Part 1b pre-dose, and during part 2 pre-dose on Day 1, 7, 14, 21, 28, and 42, and then every two weeks until end of study.

Number of planned subjects: 12

Trial population:

Inclusion criteria:

1. Confirmed diagnosis of severe congenital hemophilia A or B with an inhibitor.
2. History of frequent spontaneous bleeding episodes (historical annualized bleeding rate [ABR] of ≥ 12).
3. Male, age 18 or older.
4. Agreement to use highly effective birth control throughout the study.
5. Affirmation of informed consent with signature confirmation before any trial-related activities. (Trial related activities are any procedure that would not have been performed during normal clinical management of the subject).
6. Stated willingness to comply with all study procedures and availability for the duration of the study.

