Treatment of a spontaneous or traumatic bleeding episode: Subjects will use their current bypass regimen for any spontaneous or traumatic bleed that occurs while on study drug. If treatment for a spontaneous or traumatic bleeding episode is needed, then subjects will contact the clinical investigative team immediately to report the event, treatment dose administered, and determine follow-up plans for that event including whether to arrange for a blood specimen to be drawn (if feasible) before further administration of either study drug or the bypassing agent used for treatment. Decision whether to continue daily study drug administration will also be determined by the clinical study team after discussion with the Sponsor. See **Section 6.1.2, Dosing and Administration**, for details on dose escalation, dose de-escalation, and treatment interruption. This information will also be recorded in the subjects' diary.

Dose interruption and surgery: Daily SC study injections will be interrupted if there is a need for a surgical procedure; an event requiring extended (>48 hours) hospitalization; a thrombotic event; clinical evidence of inhibitor formation; or laboratory results suggesting an antibody may be developing.

MAA-201 VERSION 2.0

Measurements:

MarzAA antigen and activity levels and coagulation parameters will be measured at Day 1 (Pre-dose and Post-dose Hour 7), Day 3 (Pre-dose), Day 5 (Pre-dose), Day 7 (Pre-dose and Post-dose Hour 7).

If no spontaneous bleeding occurs at the first dose level in Part 2 of the study, trough antigen and activity and coagulation parameters will be measured on days 14, 21, 28, and 50 after starting their dosing regimen.

If spontaneous bleeding occurs after the fifth daily dose on a dose level, MarzAA antigen and activity levels will be measured within 6 hours of the spontaneous bleed (if feasible). Specimens for coagulation and immunogenicity testing will also be drawn.

Once it is determined to escalate to the next dose level, a pre- and 7 hours post-dose specimen will be drawn for PK, coagulation, and thrombogenicity markers on Day 7 after the dose has been escalated to estimate the new trough and peak concentrations and PD. MarzAA antigen and activity levels and coagulation parameters will then be measured (pre-dose) at Day 14, 21, 28, and 50 after dose escalation.

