### 9.1 PK SAMPLING SCHEDULE

PK sampling schedule will be specific to each part and dose administration. The PK data will be measured as MarzAA antigen concentration and activity levels. Additional PK data will include FVII, FVIIa activity.

Part 1a - single IV dose of 18 µg/kg MarzAA. PK sampling - predose, and post-dose at 5 and 30 minutes and Hour 1, 3, 6, 9, 12, and 24.

Part 1 b - single SC dose of 30 µg/kg MarzAA. PK sampling - pre-dose and Hour 3, 5, 7, 9, 12, 24, 30, and 48 post-dose.

Part 2 - daily SC dosing with variable dose to be determined.

PK sampling - Day 1 (Pre-dose and Post-dose Hour 7), Day 3 (Pre-dose), Day 5 (Pre-dose), Day 7 (Pre-dose). In the absence of spontaneous bleeding for the first dose level in Part 2 of the study, trough antigen and activity will be measured on days 14, 21, 28, and 50.

In case of spontaneous bleeding the PK samples will be taken within 6 hours of the spontaneous bleed and a pre- and 7 hours post-dose on Day 7, 14, 21, 28, and 50 after dose escalation.

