### 10.1 PD SAMPLING SCHEDULE

PD analysis includes following assessments

Coagulation assays	Thrombogenicity biomarkers
PT, aPTT, fibrinogen, and TGT	D-dimer, F1+2, and thrombin-antithrombin complexes (TAT)

PD sampling schedule will be specific to each part and dose administration.

Part 1a - single IV dose of 18 µg/kg MarzAA. PD sampling - predose, and post-dose at 5 and 30 minutes and Hour 1, 3, 6, 9, 12, and 24.

Part 1 b - single SC dose of 30 µg/kg MarzAA. PD sampling - pre-dose and Hour 3, 5, 7, 9, 12, 24, 30, and 48 post-dose.

Part 2 - daily SC dosing with variable dose to be determined.

PD sampling and assessments - Day 1 (Pre-dose and Post-dose Hour 7), Day 3 (Pre-dose), Day 5 (Pre-dose), Day 7 (Pre-dose). In the absence of spontaneous bleeding for the first dose level in Part 2 of the study, trough antigen and activity will be measured on days 14, 21, 28, and 50.

In case of spontaneous bleeding the PD samples will be taken within 6 hours of the spontaneous bleed and a pre- and 7 hours post-dose on Day 7, 14, 21, 28, and 50 after dose escalation.

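### The documents disagree on which Part 2 days the 7-hour (Cmax) sample is drawn; under SAP 9.1 the 30 µg/kg reference has no Cmax for the SAP 9.5 dose-proportionality comparison

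*SAP*

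**What the plan says.** SAP 9.2 defines Part 2 Cmax as the concentration 7 hours after the dose, so the hour-7 sampling days decide where Cmax exists.

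At 30 µg/kg:
- SAP 9.1 lists "Day 1 (Pre-dose and Post-dose Hour 7), Day 3 (Pre-dose), Day 5 (Pre-dose), Day 7 (Pre-dose" and closes the bracket there, so Day 7 has no post-dose sample. Days 14 to 50 are trough only. SAP 10.1 gives the same schedule for pharmacodynamics, beginning "PD sampling and assessments - Day 1 (Pre-dose and Post-dose Hour 7".
- Protocol 1.1 lists "Day 3 (Pre-dose), Day 5 (Pre-dose), Day 7 (Pre-dose and Post-dose Hour 7" in addition to Day 1, and Protocol 4.1 agrees: "Day 7 (Pre-dose and Post-dose Hour 7".
- SAP 3.6 has hour 7 on Days 1, 3, 5 and 7.
- The footnote to Table 3, in both documents, itemises Days 3, 5 and 7 as pre-dose only. Its opening sentence is garbled in the text available.

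After escalation:
- SAP 9.1 has "a pre- and 7 hours post-dose on Day 7, 14, 21, 28, and 50 after dose escalation". SAP 10.1 and the Table 4 footnote in both documents agree.
- Protocol 1.1 and 4.1 and SAP 3.6 have hour 7 on Day 7 only, with the later days pre-dose.

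SAP 9.5 fits a repeated-measures model to log Cmax/D and log Cmin/D, with visit (Days 7, 14, 21, 28, 50) and treatment as fixed effects and subject as random effect. On the contrasts it says: "Pair-wise comparisons will be made between test dose levels of 60, 90 and 120 µg/kg and the reference dose group of 30 µg/kg". Its minimum-data rule reads "The comparison will be performed for at least 2 dose levels with at least 6 subjects of PK data available", followed by a bracket naming Cmin or Cmax "values for each time point".

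**The concern.** A contrast against a reference dose needs data at that dose on a day the model uses. Day 1 is not a SAP 9.5 model day, so a schedule with hour 7 on Day 1 only leaves the 30 µg/kg group, which every subject who starts Part 2 enters, without any Cmax in the model. The accumulation ratio for Cmax, which SAP 9.2 defines against Day 1, would likewise have no later day at 30 µg/kg.

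The problem would be one of scheduling, not of chance missingness, and a draw that was not scheduled cannot be recovered at analysis. Correcting SAP 9.1 alone would not settle it. Under Protocol 4.1 Cmax exists on a single model day, which suits neither a repeated-visit model nor a minimum-data rule stated per time point. After escalation the two schedules differ by four hour-7 draws per dose level (Days 14, 21, 28 and 50).

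**Working it through.** The plan gives no sample-size or power figure for this analysis, so there is none to reproduce. The check is a count and an estimability test.

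**Step 1. Model days with Cmax.** Intersect each hour-7 schedule with Days 7, 14, 21, 28 and 50.

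| Source | Hour 7 at 30 µg/kg | Model days with Cmax, 30 µg/kg | Hour 7 after escalation | Model days with Cmax, escalated doses |
|---|---|---|---|---|
| SAP 9.1, 10.1 | Day 1 | 0 of 5 | Days 7, 14, 21, 28, 50 | 5 of 5 |
| Protocol 1.1, 4.1 | Days 1, 7 | 1 of 5 | Day 7 | 1 of 5 |
| SAP 3.6 | Days 1, 3, 5, 7 | 1 of 5 | Day 7 | 1 of 5 |
| Table 3 (itemised list) and Table 4 footnotes | Day 1 | 0 of 5 | Days 7, 14, 21, 28, 50 | 5 of 5 |

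Pre-dose samples exist on all five model days under every schedule, so Cmin/D is not affected.

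**Step 2. Estimability.** Write the fixed part as E[log(Cmax/D)] = μ + τ(dose) + v(visit). A contrast τ(d) − τ(30) is estimable only if it is a linear combination of the dose-by-day cells that have data.
- SAP 9.1: no cell contains τ(30). None of the 3 contrasts against 30 µg/kg is estimable. The subject random effect does not help, because no observation carries the 30 µg/kg mean.
- Protocol 4.1: the cells are μ + τ(d) + v(7) for d = 30, 60, 90 and 120. Subtracting the 30 µg/kg cell gives τ(d) − τ(30) directly, so 3 of 3 are estimable. Visit has one level and merges with the intercept, leaving a Day 7 comparison. SAP 3.6 gives the same result.
- Protocol 4.1 at 30 µg/kg with Table 4 after escalation: 3 of 3.
- SAP 9.1 at 30 µg/kg with Day 7 only after escalation: 0 of 3.
- Contrasts among 60, 90 and 120 µg/kg: 3 of 3 under every schedule.

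A rank check on the design matrix confirms these counts. This is algebraic estimability and assumes that each dose level has some subjects.

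**Step 3. The minimum-data rule.** It can be read two ways. If Cmin values alone satisfy it, it can be met under every schedule, and the Cmax model under Protocol 4.1 still has one visit. If each Cmax comparison needs Cmax on each model day, 30 µg/kg fails under all the schedules tabulated above (0 or 1 of 5 days).

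**Step 4. Would a test dose reach 6 subjects?** The documents give no escalation rate, so this is an assumption shown as a range. Take 12 subjects, no dropout, one constant spontaneous rate at every dose, and 45 at-risk days (fifth dose to Day 50). Then P(escalate) = 1 − exp(−ABR × 45/365), and the Day 7 sample at 60 µg/kg is kept with probability exp(−ABR × 2/365).

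| Assumed spontaneous ABR | P(escalate) | P(subject has Day 7 Cmax at 60 µg/kg) | P(at least 6 of 12) |
|---|---|---|---|
| 3 | 0.309 | 0.304 | 12% |
| 6 | 0.523 | 0.506 | 63% |
| 12 | 0.772 | 0.723 | 97% |

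On the same assumptions the chance for 120 µg/kg runs from about 0% to 50%. The range is too wide to say how many contrasts would be lost in practice.

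**The case against.** Four objections have force.

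First, a reader might infer that the minimum-data rule cancels the Cmax/D comparison even with Protocol 4.1 sampling. The wording does not support that as fact. It names Cmin or Cmax, and Cmin is available on every model day. Cancellation is one reading; what stands is that the rule is ambiguous and fits a single-day Cmax badly.

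Second, a reader might infer that SAP 9.1 is an undeclared departure from the protocol, since SAP 9.6 and SAP 14 list no sampling change. But SAP 9.1 matches the legible part of the protocol's own Table 3 footnote and its Table 4 footnote, and Protocol 8.2 and 8.2.4 send sites to those tables. The conflict therefore starts inside the protocol. Because the Table 3 footnote opens with a garbled sentence, it should be checked against the original and cannot settle the question either way.

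Third, the plan has some protection. SAP 9.5 runs only if there are enough data, the Cmax accumulation ratio is calculated where possible, and SAP 6.3 organises data by the protocol's scheduled visits. A Day 7 hour-7 sample drawn under Protocol 4.1 would not be discarded because SAP 9.1 omits it. This protects samples that were taken; it does not tell a site which schedule to follow.

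Fourth, SAP 3.6 adds little. Its Day 3 and Day 5 hour-7 draws are among those the protocol's summary of changes lists as deleted, so it appears to carry the superseded schedule, and it gives the same count as Protocol 4.1.

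It would also be too strong to name a number of contrasts at stake. The percentages above assume the same bleeding rate at every dose, whereas escalation exists to find a dose that lowers it.

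**Conclusion.** The inconsistency is real and its impact is minor. If SAP 9.1 describes what was drawn, 0 of 3 Cmax/D contrasts against 30 µg/kg can be estimated, and the Cmax accumulation ratio at 30 µg/kg has no day after Day 1. If Protocol 4.1 was followed, 3 of 3 can be estimated, from Day 7 only, and whether the minimum-data rule lets them run depends on how it is read.

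Dose proportionality is a conditional SAP analysis, not a named objective or endpoint. Cmin/D, the trough accumulation ratio, bioavailability and the primary ABR test do not depend on this conflict. The counts rest on SAP 9.2's hour-7 definition of Cmax and on the SAP 9.5 visit list as written. Only the chance of reaching 6 subjects rests on assumed bleeding rates.

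**What to change.** 1. In Protocol Table 3 and in SAP 3.6, 9.1, 10.1 and Table 3, set hour 7 at 30 µg/kg to Days 1 and 7, as in Protocol 4.1.
2. State one post-escalation hour-7 schedule that includes Day 7, identically in both documents (Protocol 1.1, 4.1 and Table 4; SAP 3.6, 9.1, 10.1 and Table 4).
3. In SAP 9.5, base the Cmax/D comparison with 30 µg/kg on Day 7. Require at least 6 subjects with Day 7 Cmax at 30 µg/kg and at the test dose, in place of a rule per time point.
4. Run the Day 7 to 50 Cmin/D model in all cases under its own minimum-data rule. If the Cmax rule is not met, report Cmin/D alone.
5. Summarise any later post-escalation Cmax values descriptively.

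The cost is wording in both documents. Items 1 and 3 need no draw beyond Protocol 4.1; a site that was following the Table 3 footnote would add one hour-7 sample on Day 7.

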**Statistical Analysis Plan**

Catalyst Biosciences, Inc. Protocol # MAA-201

**Version 2.0**

**Syneos Health #1009647**

- Ratio =  $100 \times e^{\text{Difference}}$
- $(1-2*\alpha)*100\%$  CIs for the Ratio:
  - Lower =  $100 \times e^{(\text{Lower Bound } (1-2*\alpha) \% \text{ CIs for the Difference})}$
  - Upper =  $100 \times e^{(\text{Upper Bound } (1-2*\alpha) \% \text{ CIs for the Difference})}$

Dose proportionality will also be explored graphically:

Box and whiskers plots of dose normalized PK parameters with treatments on X axisaxis. If simultaneous comparison of multiple dose numbers is required, the treatment and dose number combination may be presented on X axes

## 9.6 DEVIATION FROM ANALYSES PLANNED IN PROTOCOL

The PK population was added to the analysis populations.

Statistical Analysis Plan

Catalyst Biosciences, Inc. Protocol # MAA-201

Version 2.0

Syneos Health #1009647

## 10. ANALYSIS OF PHARMACODYNAMICS

PD analysis will be performed using SAS statistical packaged version 9.3 or higher. PD analysis will be performed for PD population as defined in the Section 5.6 of the SAP. PD parameters may be derived using Phoenix WinNonLin or SAS software packages.

### 10.1 PD SAMPLING SCHEDULE

PD analysis includes following assessments

Coagulation assays	Thrombogenicity biomarkers
PT, aPTT, fibrinogen, and TGT	D-dimer, F1+2, and thrombin-antithrombin complexes (TAT)

PD sampling schedule will be specific to each part and dose administration.

Part 1a - single IV dose of 18 µg/kg MarzAA. PD sampling - predose, and post-dose at 5 and 30 minutes and Hour 1, 3, 6, 9, 12, and 24.

Part 1 b - single SC dose of 30 µg/kg MarzAA. PD sampling - pre-dose and Hour 3, 5, 7, 9, 12, 24, 30, and 48 post-dose.

Part 2 - daily SC dosing with variable dose to be determined.

PD sampling and assessments - Day 1 (Pre-dose and Post-dose Hour 7), Day 3 (Pre-dose), Day 5 (Pre-dose), Day 7 (Pre-dose). In the absence of spontaneous bleeding for the first dose level in Part 2 of the study, trough antigen and activity will be measured on days 14, 21, 28, and 50.

In case of spontaneous bleeding the PD samples will be taken within 6 hours of the spontaneous bleed and a pre- and 7 hours post-dose on Day 7, 14, 21, 28, and 50 after dose escalation.

### 10.2 PLASMA PD ENDPOINT

PD parameters will be derived by non-compartmental analysis using intravascular or extravascular trapezoidal log-linear rule.

The following PD parameters will be derived for Parts 1a, 1b and 2 of the study:

$E_{max}$ or $E_{min}$	Maximum or minimum effect depending on the direction of change in PD result
$CFB_{max}$ or $CFB_{min}$	Maximum or minimum change in baseline for the effect depending on the direction of change in PD result
$TE_{max/min}$	Time to max or min value of the effect

**Statistical Analysis Plan**

Catalyst Biosciences, Inc. Protocol # MAA-201

Version 2.0

Syneos Health #1009647

AUE and AUE CFB	Area under curve effect vs time profile for actual measurements and change from baseline
TA_AUE and TA_AUE CFB	Time adjusted area under curve effect vs time profile for actual measurements and change from baseline

The PD parameters will be estimated as follows:

The apparent  $E_{max}$  and the corresponding  $CFB_{max}$  and  $T_{max}$  will be read directly from the PD value-time plot (observed data, not predicted data by the program);

AUEs will be calculated using the linear-log trapezoidal rule both for measured data and change from baseline;

TA\_AUE will be estimated as AUE divided by the time elapsed from assessment.

The parameters will be derived for the complete duration of treatment starting from the dose in Parts 1a and 1 b and from the first injection for each dose level in Part 2 of the study.

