3.2 SECONDARY

- To determine the PK and PD, of SC administration of MarzAA in patients with hemophilia with inhibitors and compare IV versus SC administration of MarzAA regarding PK, PD, and safety parameters.
- To find the optimal dose of MarzAA for each subject, ie, the dose that prevents spontaneous bleeding*; and determine the PK, PD, and safety of daily SC administration of MarzAA at the optimal dose for each subject for an extended duration, mimicking the intended SC prophylactic use of MarzAA in patients with hemophilia.
- To determine occurrence of and categorize breakthrough bleeds requiring escalation to higher dose level as follows:
 - Number of bleeds that are life threatening
 - Number that require hospitalization and/or blood transfusion
 - Number of muscle bleeds
 - Median time to resolution (and interquartile range) of bleeds

*A spontaneous bleeding episode is defined as one that is precipitated by normal ADL.

MAA-201 VERSION 2.0

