#### 3.2 SECONDARY OBJECTIVE(S)

- To determine the pharmacokinetics (PK) of SC MarZAA
- To determine the bioavailability of MarZAA when given via SC
- To determine the pharmacodynamics (PD) of SC MarZAA
- To evaluate and compare the levels of thrombogenicity markers following administration of a SC dose of 30 µg /kg MarZAA with the IV dose of 18 µg/kg MarZAA
- To evaluate for evidence of the development of antibodies to MarZAA, wild type recombinant factor VIIa (wt-rFVIIa), and/or wt-FVII, and to determine if these are neutralizing antibodies
- To determine the annualized bleeding rate (ABR) during MarZAA treatment compared to the rate of historic on-demand treatments

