### 10.3.2 Listing and Presentation of Individual PD Results

The actual assessment time or sampling for PD biomarkers will be listed for each subject in both parts of the study and will include the deviation in time from the protocol scheduled time, if applicable. Both actual measurements and change from baseline for each parameter will be presented. Baseline value will be defined as the last available value of PD biomarker before the 1st dose of the drug for part 1a, part 1b and part 2 separately.

Subjects with protocol deviations affecting PK may be flagged and excluded from summaries.

Individual PD actual measured and change from baseline data will be listed by subject, time point and treatment (in relevant concentration units) separately for Parts 1 and 2. For Part 2 the time from start of 1st dose level and time elapsed from dose escalation as well as actual dose used will be presented in the listing.

The PD results and change from baseline will be summarized at each time point by actual treatment. For the Part 2 of the study this summary will be grouped by actual dose level administered taking into account dose escalation history.

Individual PD parameters for Parts 1a and 1b will be listed for the PD population and will be summarized by treatment. Individual PD parameters for Part 2 will be listed separately for each dose level.

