### 12.3 ADVERSE EVENTS / ADVERSE DRUG REACTIONS

Adverse events will be coded using MedDRA Version 20.1 to classify events under primary SOC and PT.

A treatment emergent adverse event (TEAE) is defined as an AE that either begins after the first dose of study drug in this study or worsens after the first dose of study drug in this study but not later than the date of last dose + 30 days.

TEAEs will be assigned to each study part (part 1 or part 2) if the start date of the TEAE is after the first dosing date/time in part 1 or first date of dosing in part 2 for each dose level. TEAEs will be summarized for part 1 and 2 and different dose levels in part 2.

Number of subjects per TEAE and number of events per TEAE below will be summarized by SOC, PT and by study part/dose level. Multiple occurrences of an AE are counted only once per subject per SOC and PT for summary tables:

- Incidence of all TEAEs
- Incidence of all TEAEs by maximum severity (in the following order: severe, moderate and mild). Missing severity will be considered as severe.

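### PD area measures cover 24 h after IV but 48 h after SC, and TEAE tables pool the two single doses, so neither output serves the stated IV-versus-SC comparison

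*SAP*

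**What the plan says.** **The comparison.** Protocol 3.2 lists as a secondary objective to "compare IV versus SC administration of MarzAA regarding PK, PD, and safety parameters", and Protocol 4.1 gives this as the purpose of Parts 1a and 1b. SAP 3.2 adds: "To evaluate and compare the levels of thrombogenicity markers following administration of a SC dose of 30" µg/kg, set against the IV dose of 18 µg/kg.

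**The PD windows.** SAP 10.1 gives, for Part 1a (IV): "PD sampling - predose, and post-dose at 5 and 30 minutes and Hour 1, 3, 6, 9, 12, and 24". For Part 1b (SC) it gives: "PD sampling - pre-dose and Hour 3, 5, 7, 9, 12, 24, 30, and 48 post-dose". SAP 10.2 defines AUE and AUE_CFB (area of the measured values and of the change from baseline) and their time-adjusted versions TA_AUE and TA_AUE_CFB. The window rule is: "The parameters will be derived for the complete duration of treatment starting from the dose in Parts 1a and 1 b". TA_AUE "will be estimated as AUE divided by the time elapsed from assessment". No common window is defined. SAP 10.3.2 states: "Individual PD parameters for Parts 1a and 1b will be listed for the PD population and will be summarized by treatment".

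**The adverse events.** SAP 12.3 assigns each TEAE to one of two study parts, part 1 or part 2, and then: "TEAEs will be summarized for part 1 and 2 and different dose levels in part 2". Only Part 2 is subdivided.

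**The concern.** Every subject receives both single doses, and the plan says that the two routes will be compared. The area measures are then reported by treatment, so a 24 h IV area and a 48 h SC area appear as the results for the two routes. The markers have a non-zero natural level, so a raw area grows with the length of the window even when the drug does nothing. Dividing by time repairs that but creates the opposite problem for the change from baseline: the SC average includes hours 24 to 48, for which there is no counterpart after IV alone.

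The two errors run in opposite directions. Raw AUE makes SC look larger and TA_AUE_CFB makes it look smaller. For D-dimer, F1+2 and TAT the second is the less cautious error, because SC is the route intended for prophylaxis.

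For safety, one Part 1 block covers both doses and about 24 + 48 = 72 h. A reader of the TEAE tables cannot tell which events followed which dose.

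**Working it through.** The plan states no figure to reproduce here. The check applies the same marker profile to the two windows, T = 24 h (Part 1a) and T = 48 h (Part 1b), both from SAP 10.1 and 10.2. The TA_AUE divisor is read as the window length, since the SAP wording is loose.

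**1. Flat marker at level c (no assumption about drug effect).** AUE = c × T.
- Raw AUE, SC/IV: 48c / 24c = 2.0.
- TA_AUE, SC/IV: c / c = 1.0.
- AUE_CFB and TA_AUE_CFB are zero for both routes.

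**2. All excess area A falls in the first 24 h (limiting case).**
- AUE_CFB, SC/IV: A / A = 1.0.
- TA_AUE_CFB, SC/IV: (A/48) / (A/24) = 0.5.

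**3. Identical effect curves after both doses, illustrative shapes.** The half-lives are borrowed from the protocol: about 3.5 h for IV MarzAA (Protocol 2.2.2) and 12.4 h for SC wild-type rFVIIa (Protocol 2.2.1). They are drug half-lives used as assumed shapes for the marker effect. For exponential decay with half-life h, the area to T is proportional to 1 − 2^(−T/h). The 48 h to 24 h ratio is therefore 1 + 2^(−24/h), and the time-adjusted ratio is half of that.
- h = 3.5 h: 1 + 0.009 = 1.01; time-adjusted 0.50.
- h = 12.4 h: 1 + 0.261 = 1.26; time-adjusted 0.63.

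For rise-and-fall curves (difference of two exponentials, the same half-lives, assumed absorption rate 0.1 or 0.3 per h), the curves were integrated numerically. For raw values, a rise of 20% to 100% of baseline that decays with the same half-lives was added to a baseline of 1.

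| Measure | Profile | SC/IV ratio from window length alone |
|---|---|---|
| Raw AUE | flat | 2.00 |
| Raw AUE | baseline plus decaying rise | 1.74 to 1.96 |
| TA_AUE | flat | 1.00 |
| TA_AUE | baseline plus decaying rise | 0.87 to 0.98 |
| AUE_CFB | decay | 1.01 to 1.26 |
| AUE_CFB | rise-and-fall | 1.02 to 1.64 |
| TA_AUE_CFB | decay | 0.50 to 0.63 |
| TA_AUE_CFB | rise-and-fall | 0.51 to 0.82 |

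With a common 0–24 h window, every one of these ratios is 1.00.

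**4. TEAEs.** No arithmetic applies. SAP 12.3 also refers to counts by study part and dose level, but in that section study part means part 1 or part 2. SAP 7.1, in contrast, reports disposition separately for Parts 1a, 1b and 2, and SAP 6.3 labels analysis visits as Part 1a or Part 1b. The finer split is therefore already in use elsewhere in the SAP.

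**The case against.** A reader might infer that the Part 1 rules cannot support the IV-versus-SC comparison at all. The documents do not bear that out:
- SAP 10.2 also derives the maximum or minimum effect, the maximum or minimum change from baseline, and the time to maximum effect.
- SAP 10.3.2 summarises PD values by time point and treatment and puts the IV and SC mean curves in one figure. Pre-dose and hours 3, 9, 12 and 24 are sampled after both doses.
- SAP 9.2 computes bioavailability from AUC extrapolated to infinity and adjusted for dose, so the unequal windows do not enter.
- Laboratory, vital-sign and ECG summaries are by study part and visit.

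The SAP objective speaks of marker levels, and no section specifies an SC/IV ratio of areas. The models in SAP 10.5 use the time-adjusted areas, not raw AUE. All of this stands and limits the reach of the point.

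Two further inferences fail. The factor of 2.0 does not apply to all area measures: it concerns raw AUE, which the SAP already pairs with TA_AUE. The 0.5 is a limiting case, not an expected value.

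Nor does giving both doses to each subject make a clean paired comparison available. The doses differ (18 and 30 µg/kg), the order is fixed, and SC follows IV after 24 h. The PD baseline is reset for Part 1b, and Protocol Table 2 lets the Part 1a Hour 24 assessment serve as the Part 1b pre-dose one. With a 3.5 h half-life, only 2^(−24/3.5) = 0.9% of the drug would remain at 24 h under simple decay, but a marker response may last longer than the drug.

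On TEAEs, no information is lost: onset times are collected (Protocol 8.5.4) and all AEs are listed (SAP 12.3). The gap is in the tables. What the objection does not answer is that areas over 24 h and 48 h are summarised by route, and that no TEAE table separates the two doses.

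**Conclusion.** The concern holds in a limited form. The PD area measures are not comparable between routes as SAP 10.2 defines them. Raw AUE is inflated 2.0-fold after SC for a marker that does not move, and this figure needs no assumption. TA_AUE corrects it for a flat marker and nearly does so for modest rises. TA_AUE_CFB is biased downward after SC: 0.5 in the limiting case, and 0.50 to 0.82 over the illustrative effect shapes, which are assumptions. AUE_CFB is little affected when the effect ends within 24 h and more so when it persists.

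SAP 12.3 as written merges TEAEs after IV and after SC. The outputs affected are secondary and descriptive; the primary bleeding-rate analysis and the bioavailability estimate are untouched. This is an inexpensive correction to rules that otherwise give non-comparable or merged results for a stated objective.

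**What to change.** **SAP 10.2.** Add AUE, AUE_CFB and TA_AUE_CFB over 0–24 h for Parts 1a and 1b, with 24 h as the divisor for the last. Name these as the area measures for the route comparison, and keep the 0–48 h areas to describe SC. If a within-subject SC/IV ratio or difference is reported, label it descriptive and state that dose, order and possible carry-over are confounded with route.

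**SAP 12.3.** Tabulate TEAEs as Part 1a (IV dose to SC dose), Part 1b (SC dose to first Part 2 dose) and Part 2 by dose level. Add a footnote giving the unequal window lengths and stating that Part 1b events follow an IV dose in the same subject.

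**Cost.** SAP wording and a few table columns; all samples and onset times are already collected. There are two small downsides. The 0–24 h area omits any SC effect after 24 h, which the retained 0–48 h area still shows. Late events from the IV dose are counted under Part 1b, which the footnote discloses.
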